2. STUDY OBJECTIVES

2.1 PRIMARY OBJECTIVE

To evaluate the efficacy of belumosudil compared to placebo for the Combined Response Index in diffuse cutaneous Systemic Sclerosis (CRISS) at Week 24

2.2 SECONDARY OBJECTIVES

- To assess the CRISS for each group at Week 52
- To evaluate the efficacy of belumosudil compared to placebo at Week 24 for:
 - o mRSS
 - o FVC
 - Physician Global Assessment
 - o Patient Global Assessment
 - Scleroderma Health Assessment Questionnaire—Disability Index (SHAQ-DI)
- To evaluate the efficacy of belumosudil at Week 52 compared to baseline for subjects randomized to belumosudil for the parameters in the bullet above
- To assess changes in lung fibrosis, via high resolution computerized tomography (HRCT), performed at baseline, Weeks 24 and Week 52 only in subjects with ILD at screening
- To assess pharmacokinetics (PK) of belumosudil by sparse sampling of belumosudil on of Weeks 4 and 8 (i.e., Days 29 and 57) immediately prior to belumosudil dosing and 3 hours post-dose
- To assess the safety of belumosudil compared to placebo in subjects with dcSSc by examining the percentage of subjects with TEAEs (CTCAE v5.0) in subjects with dcSSc

2.3 EXPLORATORY OBJECTIVES

- To evaluate changes in biomarkers of endothelial cell dysfunction, fibrosis, immune system function, and cytokine alterations from subjects receiving belumosudil or placebo
- To assess histology and gene expression from skin biopsies taken from subjects at baseline, Week 24 and optionally at Week 52

3. INVESTIGATIONAL PLAN

3.1 STUDY DESIGN

This is a phase 2, placebo-controlled, double-blinded, randomized, multicenter trial in subjects with dcSSc with an open-label extension.

The duration of the study will be approximately 14 months (4 weeks for screening, 52 weeks of dosing period, and 4 weeks of Follow-up). The study will be double-blinded for the first 28 weeks followed by an open-label extension of 24 weeks.

Subjects who have signed an IRB/IEC-approved informed consent form (ICF) and met all of the inclusion/exclusion criteria will be enrolled. A total of 60 subjects will be randomized into 3 groups (1:1:1) to receive orally administered belumosudil 200 mg QD (n = 20), belumosudil 200 mg BID (n = 20), or matched placebo (n = 20) for 28 weeks. The study will be double-blinded for the first 28 weeks followed by an open-label extension of 24 weeks. After unblinding, the subjects in Group 1 and 2 will continue on the same belumosudil dose whereas the subjects in the placebo group will be re-randomized to one of the belumosudil doses (200 mg QD or 200 BID) in 1:1 fashion.

Subjects will undergo evaluations as outlined in the Study Assessment Tables in Appendix A.

[figure not shown]
Efficacy will be assessed throughout the 52-week dosing period using CRISS, mRSS, PFTs, physician global assessment, and patient global assessments.

Follow-up Period

A 4-Week Safety Follow-Up visit will occur $28 (\pm 3)$ days after the last dose of study drug. Subjects will undergo PEs; vital sign measurements; weight measurement; blood sample collection for hematology and chemistry; thyroid function: urinalysis; ECGs; AE assessments; concomitant medication assessments; and pregnancy testing for females of childbearing potential. In addition, patients will also have efficacy assessments done as per Appendix A.

Page 32 of 99

Figure 1 Schematic of Study KD025-209

3.2 Number of Subjects

Sixty male and female subjects will be enrolled (20 randomized to each of the 2 belumosudil dose groups and the placebo group).

3.3 STUDY CENTERS

Approximately 25 centers will participate in this study.

3.4 INCLUSION CRITERIA

- Male and female subjects ≥ 18 years old with the diagnosis of dcSSc according to the 2013 American College of Rheumatology and European League Against Rheumatism criteria
- 2. Must have disease duration (defined as interval from first non-Raynaud disease manifestation) of ≤ 5 years
- 3. Must have mRSS of \geq 15 but \leq 35
- 4. Active disease defined as any of the following within the 6 months prior to screening:
 - a. Increase in mRSS by ≥ 3 units
 - b. Increase in mRSS by ≥ 2 units with involvement of 1 new body area
 - c. Involvement of 2 new body areas

Page 33 of 99

27 May 2021

- d. Symptoms indicative of skin activity such as severe cutaneous itching or burning
- 5. Subjects receiving concomitant immunosuppression must be on a stable dose for at least 3 months prior to screening
- 6. Adequate organ and bone marrow functions evaluated during the 28 days prior to enrollment as follows:
 - a. Absolute neutrophil count $\geq 1.5 \times 10^9/L$
 - b. Platelet count $\geq 100 \times 10^9/L$
 - c. Total bilirubin $\leq 1.0 \times$ upper limit of normal (ULN)
 - d. Alanine aminotransferase (ALT), aspartate aminotransferase (AST), and serum creatinine $\leq 1.5 \times ULN$
- 7. Female subjects of childbearing potential have a negative pregnancy test at screening. Females of childbearing potential are defined as sexually mature women without prior hysterectomy or who have had any evidence of menses in the past 12 months. However, women who have been amenorrheic for 12 or more months are still considered to be of childbearing potential if the amenorrhea is possibly due to prior chemotherapy, anti-estrogens, or ovarian suppression.
 - a. Women of childbearing potential (i.e., menstruating women) must have a negative urine pregnancy test (positive urine tests are to be confirmed by serum test) documented within the 24-hour period prior to the first dose of study drug.
 - b. Sexually active women of childbearing potential enrolled in the study must agree to use 2 forms of accepted methods of contraception during the course of the study and for 3 months after their last dose of study drug. Effective birth control includes (i) IUD plus 1 barrier method; (ii) on stable doses of hormonal contraception for at least 3 months (e.g., oral, injectable, implant, transdermal) plus 1 barrier method; or (iii) two barrier methods. Effective barrier methods are male or female condoms, diaphragms, and spermicides (creams or gels that contain a chemical to kill sperm), or a vasectomized partner.
- 8. For male patients who are sexually active and who are partners of premenopausal women: agreement to use 2 forms of contraception as in Criterion Number 7 above during the treatment period and for at least 3 months after the last dose of study drug.
- 9. Male subjects must not donate sperm for 3 months after last dose of study drug.

10. Able to provide written informed consent prior to the performance of any study-specific procedures.

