5.2.1 Week 1, Day 1 Visit (Baseline)

At the Week 1 Day 1 visit, subjects will come to the clinic to have the following procedures:

- Confirmation of inclusion/exclusion criteria
- Randomization
- mRSS
- SHAQ-DI
- Physician Global Assessment
- Patient Global Assessment
- Pulmonary function test (PFT)*
- HRCT (± 7 days; for subjects with ILD at screening only)
- Skin biopsies
- Sampling for PD
- Complete PE
- Vital signs
- Weight
- Hematology and chemistry*
- Urinalysis*
- 12-lead ECG
- Pregnancy test
- Dispense study diary
- Study drug administration review with patient
- Dispense study drug
- Concomitant medication assessment
- AE assessment

*If these assessments were conducted within seven (7) days of baseline, they do not need to be repeated.

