6.2.5 Pregnancy Testing

Pregnancy tests (urine) will be done in women of childbearing potential. Positive urine results are to be confirmed with serum testing. In the event of a positive urine test at baseline, serum testing results should be acquired within 48 hours prior to study start.

In the event that a subject or subject's partner becomes pregnant while on study, they will be monitored until the outcome of the pregnancy is known. The baby will continue to be monitored to 30 days after delivery. The data are reported on a pregnancy form within 24 hours of becoming aware.

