- h. A complete PE is to include documentation of height (screening only), weight, body temperature, and vital signs (blood pressure [sitting], pulse rate [sitting], and respiratory rate) and will be performed by a physician or staff member who is qualified to perform such examinations (e.g., physician assistant, nurse practitioner). All PEs, whether complete or symptom-directed, will include assessment of cardiac (including heart rate and vital signs), musculoskeletal (i.e., muscle aches), and neurological (i.e., gait) systems. A complete PE include will include evaluation of primary endpoints.
- i. Sitting blood pressure, heart rate to be obtained (after 5 minutes of rest)
- j. See Section 6.2.4 for a complete list of laboratory safety assessments. If increases in liver enzymes are observed at any time in a subject, refer to Section 4.13.
- k. Women of childbearing potential must have a negative urine pregnancy test. Positive results are to be confirmed with serum testing.
- 1. Subjects will take their morning dose at the clinic and then will be dispensed study drug for home administration.
- m. Pharmacodynamics will be collected as follows: within 60 minutes pre-dose at baseline, Week 8, week 24, and Week 52. ELFT collected at Baseline, Week 8, Week 24 and Week 52.
- n. Pharmacokinetics will be collected within 60 minutes pre-dose of dosing and 3 hours post-dose with a window of 10 minutes at Week 4 and Week 8.
- o. All subjects will be un-blinded at this visit.

Note: At Week 1, Day 1 visit, if screening was completed within 7 days of baseline, only the complete PE and vital sign measurements need to be repeated.

Note: The term EOT refers to early withdrawal or Week 52, as appropriate.

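### Criterion 7a ties the 24-hour pre-dose pregnancy test to menstruating women, contradicting criterion 7, and an Appendix A note conflicts with section 5.2.1 on the Day 1 test

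*Protocol*

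**What the plan says.** Criterion 7 (Protocol section 3.4) requires a negative pregnancy test at screening for females of childbearing potential and defines the term. Any menses in the past 12 months brings a woman within it. The criterion then adds that "women who have been amenorrheic for 12 or more months are still considered to be of childbearing potential" where earlier chemotherapy, anti-estrogen treatment or suppression of the ovaries may explain the amenorrhea.

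Criterion 7a follows directly: "Women of childbearing potential (i.e., menstruating women) must have a negative urine pregnancy test", and the result must be "documented within the 24-hour period prior to the first dose of study drug". The synopsis carries the same text.

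Four other places bear on the test at the start of dosing:

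- Section 5.2.1 (Week 1, Day 1) lists "Pregnancy test" with no asterisk. Its waiver, "If these assessments were conducted within seven (7) days of baseline, they do not need to be repeated", applies to asterisked items only: the pulmonary function test, hematology and chemistry, and urinalysis.
- Section 6.2.5 assigns testing to women of childbearing potential and presumes a test at baseline: "In the event of a positive urine test at baseline, serum testing results should be acquired within 48 hours prior to study start".
- Appendix A, footnote k: "Women of childbearing potential must have a negative urine pregnancy test".
- Appendix A, closing note on repeat assessments: "if screening was completed within 7 days of baseline, only the complete PE and vital sign measurements need to be repeated".

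**The concern.** The abbreviation in 7a equates two groups; it does not give an example. A woman who has not menstruated for 12 months or more cannot be a menstruating woman, so criterion 7 and criterion 7a cannot both hold. The same is arguably true of a woman whose last period was some months ago. The extension in criterion 7 serves to keep in view women who might be assumed infertile, and 7a leaves them out of the one rule with a 24-hour limit.

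The Appendix A note is a second, separate conflict: read literally, it drops a Day 1 test that section 5.2.1 does not allow to be waived.

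What is at stake is subject safety, not inference. Section 1.3 reports embryo-fetal toxicity and teratogenicity in nonclinical studies. Section 3.3 plans about 25 centers, each of which has to apply this text.

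**Working it through.** The plan gives no figure to reproduce. The check compares the texts and then works out how old the last negative test could be at the first dose.

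**Inputs**

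- First dose: Day 1, in the clinic (section 5.2.1; Appendix A, footnote l).
- Limit in 7a: 24 hours.
- Screening: Day -29 to Day -1 (section 5.1).
- Trigger for the Appendix A note: screening completed within 7 days of baseline.
- Next scheduled test after Day 1: Day 15, plus or minus 3 days (section 5.2.2).

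**Who is tested on Day 1?** Section 5.2.1 lists the test but names no population. The population comes from section 6.2.5 and footnote k. Both use the term that criteria 7 and 7a treat differently, so neither settles the matter by itself.

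**A non-menstruating woman who meets criterion 7, under three site practices**

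| Site practice | Day 1 test | Age of last negative test at first dose |
|---|---|---|
| Criterion 7 definition, section 5.2.1 followed | Done | About 0 days |
| Criterion 7 definition, Appendix A note followed | Dropped | About 7 days, or up to 29 days if tested early in screening |
| 7a wording used as the definition | Can be omitted | That of the screening test: up to 29 days |

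For a menstruating woman the second row does not arise, because 7a still requires the 24-hour test whatever the note says. For the others, as 7a is worded, it does not.

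**Arithmetic**

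- Test done 7 days before dosing: 7 × 24 = 168 h, which is 168 − 24 = 144 h (6 days) beyond the 7a limit.
- Test done on Day -29: 29 × 24 = 696 h, which is 696 − 24 = 672 h (28 days) beyond the limit.
- Next scheduled test: 15 − 1 = 14 days after the first dose; with the window, 14 − 3 = 11 to 14 + 3 = 17 days.

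Seven days is not a ceiling in the second row. The note is triggered by when screening was completed, not by when the pregnancy test was done. If screening is spread over several days, an early pregnancy test can be much older than 7 days when the note is applied.

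The third row assumes that the screening test was done, because criterion 7 requires it in the same paragraph that gives the wider definition. A site that carried the 7a wording through every visit could also question the Day 15 test for such a woman.

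**The case against.** The strongest reply is that 7a is a sub-item of criterion 7, so it naturally carries the parent definition and the parenthesis is loose shorthand. The rest of the protocol supports that reading. Criterion 7 requires a negative screening test. Day 1 includes confirmation of eligibility and a pregnancy test that cannot be waived. Section 6.2.5 presumes a baseline test, and footnote k has no restriction to menstruating women. Tests recur at Day 15 and at every later visit. Criterion 7b requires two forms of contraception for sexually active women of childbearing potential, and exclusion criterion 3 bars pregnant women. A site that follows section 5.2.1 with the criterion 7 definition has no late test at all.

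Most of this stands, and it is why the point is minor. It does not remove the contradiction. Section 6.2.5, footnote k and criterion 7b all depend on the disputed term, and the Appendix A note still conflicts with section 5.2.1.

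A reader might infer more than the documents support:

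- *That women would start treatment with no pregnancy test.* The screening test is required, and section 5.2.1 lists a Day 1 test.
- *That the gap needs the Appendix A note.* Using the 7a wording as the definition is enough on its own.
- *That the number of women affected is large, or close to zero.* The documents give no count of women who are of childbearing potential but not menstruating, so neither claim can be made.
- *That trial results are affected.* Nothing here touches an endpoint, an analysis population or a model.

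**Conclusion.** The point holds as a minor wording error in an eligibility safety rule. Criterion 7a, in section 3.4 and in the synopsis, contradicts the definition it is meant to apply, and the Appendix A note conflicts with section 5.2.1.

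The practical gap is limited and conditional. It needs a woman who is of childbearing potential under criterion 7 but not menstruating, and a site that either adopts the 7a wording as its definition or follows the Appendix A note over section 5.2.1. In that case the last negative test at first dose could be about 7 days old, or up to 29 days old if done early in screening, against the 24-hour standard. The next scheduled test comes 11 to 17 days after the first dose. These figures assume that the screening test was done as criterion 7 requires. How many women would be affected is unknown.

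**What to change.** Three wording changes:

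1. In criterion 7a of section 3.4, replace the parenthesis equating the term with menstruating women by a reference: as defined in criterion 7.
2. Make the same replacement in criterion 7a of the synopsis.
3. In the Appendix A note on the Week 1, Day 1 visit, add the pregnancy test to the items always repeated on Day 1, in line with section 5.2.1.

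The first two close the route through the definition; the third closes the route through the note. The cost is the three edits and at most a few extra urine tests. Design, sample size and analysis are unchanged.

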3.5 EXCLUSION CRITERIA

- 1. Subject has corrected QT interval using Fredericia's formula (QTcF) > 450 ms
- 2. Ongoing use or current use of concomitant medication known to have the potential for QTc prolongation;
- 3. Female subject who is pregnant or breastfeeding
- 4. Participated in another study with an investigational drug within 28 days of study entry (for studies involving biologics, within 3 half-lives of the biologic)
- 5. History or other evidence of severe illness or any other conditions that would make the subject, in the opinion of the Investigator, unsuitable for the study
- 6. Chronic heart failure with New York Heart Association Classes II, III, and IV
- 7. Acute or chronic liver disease (e.g., cirrhosis)
- 8. Positive human immunodeficiency virus (HIV) test
- 9. Active hepatitis C virus (HCV), hepatitis B virus (HBV), or positive whole blood tuberculin test
- 10. Diagnosed with any malignancy within 3 years of enrollment, with the exception of basal cell or completely resected squamous cell carcinoma of the skin, resected in situ cervical malignancy, resected breast ductal carcinoma in situ, or low-risk prostate cancer after curative resection
- 11. Has had previous exposure to belumosudil or known allergy/sensitivity to belumosudil or any other ROCK2 inhibitor
- 12. Scleroderma renal crisis within 4 months prior to enrollment
- 13. FVC < 50% Predicted

3.6 SCREENING

The screening period commences once the ICF is signed. Adequate time must be allowed for the subject to ask questions and make a voluntary decision. The ICF must be signed before any study-specific samples are taken or study-specific tests or evaluations are conducted.

Data regarding screen-failures will be captured in the electronic data capture (EDC) system.

Screening assessments as summarized in the Schedule of Assessments (Appendix A) will be performed within 29 days of first dose of study drug (Week 1, Day 1 visit).

Study eligibility will be based on satisfying all of the study inclusion and exclusion criteria.

Re-screening of subjects will be allowed only upon approval of the Medical Monitor.

3.7 WITHDRAWAL CRITERIA

Subjects may be withdrawn from study treatment at any time by the Investigator if it is considered detrimental for the subject to continue in the study. The reason for withdrawal must be captured in the eCRF.

Subjects have the right to withdraw from the study at any time and for any reason without prejudice to their future medical care by the physician or at the institution. Every effort should be made to have such subjects attend End-of-Treatment (EOT) and 28-day Follow-Up visits. In the instances where a reason for withdrawal of consent is given, this will be captured in the electronic case report form (eCRF). Subject data up to withdrawal of consent will be included in the analysis of the study, and where permitted, publicly available data can be included after withdrawal of consent.

3.8 REPLACEMENTS

Subjects withdrawn from the study before receiving any study drug will be replaced by enrolling additional subjects into the study.

3.9 TREATMENT DISCONTINUATION

Treatment discontinuation reasons include the following:

- An AE requiring permanent discontinuation of study drug
- Investigator decision
- Clinically significant disease progression. For example:
 - o mRSS increase ≥ 5 units
 - Absolute decrease in FVC (% predicted) ≥10% or absolute decrease in diffuse capacity of the lungs for carbon monoxide (DLco) (corrected for Hb) of > 15%
 - o Renal crisis
- Study stopping rules for the sponsor (Section 9.6.1)
- Subjects meeting criteria for discontinuation from the study (Section 9.6.2)

- Voluntary withdrawal by subject
- Noncompliance to protocol
- Subject lost to follow-up
- Termination of the study by sponsor
- Subject death

4. STUDY TREATMENT

4.1 INVESTIGATIONAL PRODUCT

Belumosudil (2-(3-(4-(1H-indazol-5-ylamino) quinazolin-2-yl) phenoxy)-N-isopropylacetamide-methane sulfonic acid salt) is an orally available ROCK2 selective inhibitor. Belumosudil will be provided as 200 mg tablets. Placebo oral medication will match belumosudil oral medication.

4.2 DOSAGE AND ADMINISTRATION

Subjects will be randomized to receive belumosudil 200 mg QD (Group 1), belumosudil 200 mg BID (Group 2), or matched placebo (Group 3) in the double-blinded 28 weeks as follows:

Table 2 Dosing of Treatment Groups for Double-blind Period of Study

Belumosudil Group	AM	PM
Group 1 (200 mg QD)	One 200 mg belumosudil tablet	One matched placebo
Group 2 (200 mg BID)	One 200 mg belumosudil tablet	One 200 mg belumosudil tablet
Group 3 (Placebo)	One matched placebo	One matched placebo

BID = twice daily; QD = once daily

After unblinding, the subjects in Group 1 and 2 will continue on the same belumosudil dose whereas the subjects in the placebo group will be re-randomized to one of the belumosudil doses (200 mg QD or 200 mg BID) in 1:1 fashion.

4.3 TREATMENT ASSIGNMENT

All subjects in the study will be double-blinded for the first 28 weeks and open-label for another 24 weeks.

Subjects will be randomized 1:1:1 to receive belumosudil 200 mg QD (Group 1), belumosudil 200 mg BID (Group 2), and matched placebo (Group 3) for the first 28 weeks. After unblinding, the subjects in Group 1 and 2 will continue on the same belumosudil dose whereas the subjects in the placebo group will be re-randomized to one of the belumosudil doses (200 mg QD or 200 mg BID) in 1:1 fashion. This unblinding will be done as each subject reaches 28 weeks.

4.4 BLINDING

Study will be double-blinded for the first 28 weeks and open-label for another 24 weeks.

Page 38 of 99

4.5 TREATMENT COMPLIANCE

Subjects will be given a study drug diary to record the details of each dose of study drug. Diaries will be dispensed/collected on each visit. Compliance with oral dosing will be confirmed using patient diaries, which will be examined at each visit by site staff to determine if dosing is as instructed per protocol and follow-up with the subject accordingly. If the subject skips more than 7 consecutive days of drug dosing (other than those specified in the Dose Modification Guideline for Toxicity), the subject should be discontinued from the study unless approved by the Medical Monitor and Investigator.

4.6 MISSED DOSES

Subjects should make every effort to take the study drug at the same scheduled time daily. In the event that the subject misses the planned dose of study drug, the following protocol should be followed:

For subjects during the 28 weeks of double-blinding:

- If less than 6 hours of time have elapsed after the scheduled dose, the drug should be taken. The subject should then resume the regular planned daily dosing schedule the following day.
- If ≥ 6 hours of time have elapsed after the scheduled dose, the drug should be skipped for that day. The subject should then resume the regular planned dosing schedule the following day.

For subjects during the 24 weeks of open-label:

For subjects receiving study drug on a QD dosing schedule:

- If < 12 hours of time have elapsed after the scheduled dose, the drug should be taken. The subject should then resume the regular planned daily dosing schedule the following day.
- If ≥ 12 hours of time have elapsed after the scheduled dose, the drug should be skipped for that day. The subject should then resume the regular planned dosing schedule the following day.

For subjects receiving study drug on a BID dosing schedule:

Kadmon Corporation, LLC

27 May 2021

- If < 6 hours of time have elapsed after the scheduled dose, the drug should be taken. The subject should then resume the regular planned dosing schedule.
- If \geq 6 hours of time have elapsed after the scheduled dose, the dose should be skipped and the subject should resume dosing with the next regular planned dose.

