	3. Female subject who is pregnant or breastfeeding
	4. Participated in another study with an investigational drug within 28 days of study entry (for studies involving biologics, within three half-lives of the biologic)
	5. History or other evidence of severe illness or any other conditions that would make the subject, in the opinion of the Investigator, unsuitable for the study
	6. Chronic heart failure with New York Heart Association Classes II, III, or IV
	7. Acute or chronic liver disease (e.g., cirrhosis)
	8. Positive human immunodeficiency virus (HIV) test
	9. Active hepatitis C virus (HCV), hepatitis B virus (HBV), or positive whole blood tuberculin test
	10. Diagnosed with any malignancy within 3 years of enrollment, with the exception of basal cell or completely resected squamous cell carcinoma of the skin, resected in situ cervical malignancy, resected breast ductal carcinoma in situ, or low-risk prostate cancer after curative resection
	11. Has had previous exposure to belumosudil or known allergy/sensitivity to belumosudil, or any other ROCK2 inhibitor
	12. Scleroderma renal crisis within 4 months prior to enrollment
	13. FVC \leq 50% Predicted.
Test Article(s)	Belumosudil will be provided as 200 mg tablets.
	Matching placebo will be provided during the initial double-blind period as appropriate for subjects in Group 1 and Group 3.
Dosage and Administration	Subjects will be randomized to receive belumosudil 200 mg QD (Group 1), belumosudil 200 mg BID (Group 2), or matched placebo (Group 3) in the blinded 28 weeks as follows:
	Group 1: Belumosudil 200 mg QD (one 200 mg belumosudil tablet AM and one matched placebo PM) will be administered orally daily.
	Group 2: Belumosudil 200 mg BID (one 200 mg belumosudil tablet AM and one 200 mg belumosudil tablet PM) will be administered orally daily.
	Group 3: Matched placebo (one placebo tablet AM and one placebo tablet PM) will be administered orally daily.
	After unblinding, the subjects in Group 1 and 2 will continue on the same belumosudil dose whereas the subjects in the placebo group will be re-randomized to one of the belumosudil doses (200 mg QD or 200 mg BID) in 1:1 fashion.
Reference Therapy	Not applicable.
L	

Duration of Treatment	Study drug dosing will be for 52 weeks: double-blinded for the first 28 weeks followed by an open-label extension of 24 weeks).
Concomitant Treatment	Ongoing immunosuppressive therapy with steroids \le 10 mg per day is permitted.

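### The blinded-period missed-dose rule uses once-daily wording for a twice-daily tablet schedule, so a missed morning tablet, read literally, also cancels the evening tablet

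*Protocol*

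**What the plan says.** **Schedule.** Protocol section 4.2 (Table 2) and the synopsis give every blinded subject two tablets a day. For the once-daily arm the synopsis states: "Belumosudil 200 mg QD (one 200 mg belumosudil tablet AM and one matched placebo PM) will be administered orally daily". In the twice-daily arm (Group 2) both of the day's tablets are active, and in Group 3 both are placebo.

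**Blinded rule.** Section 4.6 opens with "In the event that the subject misses the planned dose of study drug, the following protocol should be followed" and then gives one rule for all blinded subjects, with no split by arm or by morning and evening tablet. At 6 hours or more: "If ≥ 6 hours of time have elapsed after the scheduled dose, the drug should be skipped for that day", and the regular schedule restarts the next day. At less than 6 hours the late drug is taken, and the regular daily schedule again restarts the next day.

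**Open-label rules, same section.** For once-daily dosing: "If ≥ 12 hours of time have elapsed after the scheduled dose, the drug should be skipped for that day", restarting the next day. For twice-daily dosing, with a 6-hour cut-off: "the dose should be skipped and the subject should resume dosing with the next regular planned dose".

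**Compliance.** Section 4.5 states: "Subjects will be given a study drug diary to record the details of each dose of study drug". Site staff examine the diaries at each visit to see whether dosing followed the protocol.

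**The concern.** Section 4.6 gives two different instructions for the same morning-and-evening schedule, depending on whether the subject is blinded or in open label. The blinded version has the twice-daily cut-off but the once-daily consequence. Taken at its word, it cancels an evening tablet that was never missed.

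In Groups 1 and 3 the cancelled evening tablet is placebo. In Group 2 it is 200 mg of belumosudil, half the daily dose. The higher-dose arm would therefore be under-dosed for no stated reason.

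The wording also leaves room for different practice. Subjects at about 25 centers (section 3.3) could dose differently after the same missed tablet. Because staff check diaries against the protocol, a subject who takes the evening tablet after a missed morning one could be judged compliant at one site and non-compliant at another.

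**Working it through.** The plan gives no figure on this point to reproduce. The check compares the rules and then sizes the literal reading.

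**1. The rules side by side**

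| Rule in 4.6 | Tablets per day | Cut-off | What is skipped | Dosing restarts |
|---|---|---|---|---|
| Blinded, all arms | 2 | 6 h | the drug, for that day | next day |
| Open-label QD | 1 | 12 h | the drug, for that day | next day |
| Open-label BID | 2 | 6 h | that dose | next planned dose |

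The blinded row takes its cut-off from the BID rule and its consequence from the QD rule. For a missed evening tablet this does no harm, since the next tablet is due the following morning anyway. The problem is confined to the morning tablet.

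**2. Active drug lost per morning tablet missed by 6 h or more**

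| Group | Literal rule | Per-tablet rule | Avoidable loss |
|---|---|---|---|
| 1 (200 mg QD) | 200 mg | 200 mg | 0 |
| 2 (200 mg BID) | 400 mg | 200 mg | 200 mg |
| 3 (placebo) | 0 | 0 | 0 |

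**3. Gap between active doses in Group 2.** Let s be the hours from the morning to the evening tablet. The last active dose before the miss is the previous evening's.

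- Per-tablet rule: the next active dose is that evening, 24 h later.
- Literal rule: the next active dose is the following morning, 24 + (24 − s) = 48 − s hours later.
- At s = 12 (assumed) the gap is 36 h; at s = 10 it is 38 h, and at s = 14 it is 34 h.
- With the half-life of about 7 h in section 1.4.1: 36/7 = 5.1 half-lives against 24/7 = 3.4.

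**4. Cumulative loss in Group 2.** Let p be the share of morning tablets missed by 6 h or more, and r the share of evening tablets missed, independent of the morning. The documents give neither, so both are assumptions.

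- Planned drug: 168 days × 400 mg = 67,200 mg by Week 24; 196 × 400 = 78,400 mg by Week 28.
- Avoidable loss = 200 × p × (1 − r) mg per day.

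| p | r | Events by Week 24 (168p) | Loss by Week 24 | Share | Loss by Week 28 |
|---|---|---|---|---|---|
| 1% | 0 | 1.7 | 336 mg | 0.5% | 392 mg |
| 5% | 0 | 8.4 | 1,680 mg | 2.5% | 1,960 mg |
| 1% | 1% | 1.7 | 333 mg | 0.5% | – |
| 5% | 5% | 8.4 | 1,596 mg | 2.4% | – |

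These figures cover the skip bullet only. The under-6-hour bullet has the same fault and is not counted.

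**5. Direction of any distortion between doses.** The BID:QD ratio of active drug is 2 − r under the literal rule and (2 − p − r)/(1 − p) under the per-tablet rule. With p = 5% and r = 0 this is 2.00 against 2.05; with p = r = 5% it is 1.95 against 2.00. The literal rule can keep the ratio at the intended 2 or pull it below, depending on which tablets are missed, so no claim of imbalance follows.

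**The case against.** The strongest reply is that the literal reading is not the natural one. Section 4.6 is triggered by a single missed dose, and its clock runs from a single scheduled dose. An evening tablet not yet due has not been missed. In the under-6-hour bullet, the drug to be taken can only be the one late tablet, so the drug to be skipped in the next bullet should be that tablet too. Read literally, the under-6-hour bullet would let a morning tablet taken minutes late cancel the evening one, which is hardly intended. The diary records each dose, Table 2 schedules an evening tablet daily, and the 6-hour cut-off points to a twice-daily rule. The diary instructions, which are not in these documents, may already settle the matter.

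The stakes are also small. The QD arm has 24 hours between active doses every day by design, at a dose that section 1.6 associates with clinical efficacy. Section 4.12 permits dose interruptions of up to 14 days for toxicity. Nothing in the documents links one longer gap to a change in Week 24 CRISS, and variation between sites is conjecture.

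Much of this stands. A twice-daily rule was probably intended, a per-tablet reading is open to sites, and the consequence is minor. But the per-tablet reading does not explain why dosing should restart only the next day after a missed morning tablet. No missed-dose text says the evening tablet is still taken, and this text is the standard against which diaries are checked. That two readings are possible is itself a reason to correct an operative dosing instruction.

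**Conclusion.** The concern holds, at low severity. As written, the blinded rule contradicts the protocol's own rule for the same twice-daily schedule. Followed literally, it costs a BID-arm subject an avoidable 200 mg per missed morning tablet and lengthens the gap between active doses from 24 to about 36 hours, assuming tablets 12 hours apart. At assumed miss rates of 1% to 5% of mornings, with no evening misses and the literal reading followed every time, the loss by Week 24 is 0.5% to 2.5% of planned BID drug.

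The conclusion goes no further. The primary analysis is on the mITT population (SAP section 3.2) and is not threatened. No planned efficacy analysis is shown to change. The synopsis plans no formal comparison of the two doses. The gain from correcting the wording is that avoidable under-dosing is removed and sites handle a missed tablet alike.

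**What to change.** In Protocol section 4.6, replace both blinded-period bullets with the open-label twice-daily rule, stated per tablet and identically for all three arms:

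- Less than 6 hours late: take the tablet and continue the regular schedule, including that day's other tablet.
- 6 hours or more late: skip that tablet only and resume with the next planned tablet.

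Put the same wording in the diary instructions. Using one text for every arm keeps the blind. The cost is a wording change in the protocol and the diary instructions; no procedure, visit or patient is added.
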